1. PURPOSE OF THE STUDY AND BACKGROUND

1.1. Purpose of the study

The purpose of this study is to investigate the efficacy of mastoid oscillation in patients with active Ménière's disease that is not controlled by traditional medical management.

1.2. Background

Since Hallpike and Cairns first described the histologic findings of the inner ear in Ménière's disease in 1938, attention has focused on the cause for these findings. Despite reconfirmation of the histologic findings over the years, such that endolymphatic hydrops is universally accepted as synonymous with Ménière's disease, the etiology for these findings and the clinical symptoms remains elusive.

Paralleling the futile search for the cause, there has been a rich and equally frustrating history regarding the treatment of Ménière's disease. The history and literature is replete with conservative measures attempting to control symptoms without being destructive, as well as more predictable but destructive procedures for recalcitrant symptoms.

One of the more lively and ongoing debates centers around the role and the mechanism of action of endolymphatic shunt/decompression procedures. Those who espouse endolymphatic sac surgeries believe in their value and effect. Naysayers cite the natural history of the disease and the results of the foreshortened sham surgery study completed in Denmark.¹ Even proponents of endolymphatic sac surgery can't agree on the management of the sac, some shunting into the cerebrospinal fluid space, some shunting into the mastoid, some suggesting that fluid pressures can be controlled with valves and others avoiding shunting completely and merely decompressing the sacs. Interestingly, aside from mild variations, all approaches seem to produce similar results. Although foreshortened and resulting in inadequate numbers for statistical analysis, even the sham study¹ seemed to produce similar results. Is there any unifying hypothesis that would explain these observations?

Those who perform endolymphatic sac surgeries believe there is a temporal relationship between the surgical procedure and the improvement in symptoms that the patient experiences. However, the reason for the improvement is unknown. It is merely conjecture that the effect of the endolymphatic shunt is decompressive drainage through the endolymphatic duct and sac. This has never been scientifically demonstrated. In fact, the observation that decompression of the endolymphatic sac without shunting is equally effective would suggest that decompressive drainage may not be the reason that endolymphatic sac procedures work.

The one common factor in all of these surgeries is the use of the otologic drill to remove the bone of the mastoid and expose the endolymphatic sac. In fact, even in the sham study, the otologic drill was used to remove the mastoid cortex, but the surgery was not completed to expose the endolymphatic sac. What effect might the drill have on the process of Ménière's disease?

It is generally accepted that the cause of benign paroxysmal positional vertigo (BPPV) is related to particles/otoconia floating free in the endolymph of the inner ear and becoming trapped in the posterior semicircular canal. These particles have been shown to exist, both histopathologically and clinically. One of the forms of treatment for BPPV is referred to as the canalith repositioning maneuver, designed to move these particles from the posterior semicircular canal back into the endolymphatic system in the

vestibule of the inner ear, thus relieving the symptoms of positional vertigo. These particles have also been known to be trapped in the lateral semicircular canal, but have never been implicated in other forms of pathology of the inner ear.

A hypothesis has been proposed that these particles may become briefly trapped in the outflow tract of the endolymphatic duct from the inner ear (vestibulolithiasis) and thereby produce the endolymphatic hydrops that is felt to produce the symptoms of Ménière's disease. It is likewise hypothesized that, if these particles do jam the endolymphatic duct, *they might be freed by tipping the endolymphatic duct towards the vestibule of the inner ear and oscillating the temporal bone/inner ear structures.*

A pilot study (RSRB 9358) using head positioning and mastoid oscillation has been completed and the results twice reported at the American Academy of Otolaryngology-Head and Neck Surgery annual meeting^{2,3}. The results were positive with improvements comparable to the other forms of conservative surgical measures currently practiced in the treatment of Ménière's disease. The only objection to the pilot study was the lack of controls, a standard to which few other available treatments for Ménière's disease have been held. Nevertheless, the current study has been designed to attempt to address this objection.

2. STUDY DESIGN

2.1. Overview

This is a single center, randomized, placebo-controlled trial of mastoid oscillation for treatment of Ménière's disease. Eligible subjects will be randomized using a 1:1 allocation to either mastoid oscillation or placebo (oscillator device that provides the same sound but no vibration of the mastoid) received for 30 minutes at four weekly study visits, with efficacy determination via change in frequency and severity of Ménière's symptoms following the final study visit.

2.2. Rationale for Study Design

The pilot study has already determined that approximately 75% of patients undergoing mastoid oscillation for Ménière's disease refractory to medical treatment significantly improve or resolve their symptoms, compared with less than 10% in a 'waiting list' control group. This means that 75% of patients seen who here-to-fore would have had surgery or a destructive procedure offered now have a non-surgical/non-destructive option available. The ongoing debate that blocks use of this treatment routinely in treatment of patients with refractory Ménière's disease is whether this improvement is better than the natural history of the disease. Therefore, objections demand a control group/study before this form of treatment is accepted as a viable alternative before considering surgical or ablative approaches to the management of Ménière's disease refractory to medical treatment. We have now designed and will have produced a null device (control) which should address this objection/concern. This device will produce the sound of oscillation, but there will be no oscillation delivered. Therefore, the control/null device will be identical to the mastoid oscillator, except that there will be no oscillation whatsoever delivered.

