3.2. Inclusion and Exclusion Criteria

a) Inclusion Criteria:

- a. Adults aged 18 and older
- b. Clinical diagnosis of Ménière's disease, with classical symptoms:
 - i. Episodic spinning vertigo
 - ii. Fluctuating unilateral low frequency sensorineural hearing loss
 - iii. Tinnitus
 - iv. Aural fullness
- c. Failure of traditional medical management of Ménière's disease symptoms
- d. English language skills sufficient to provide informed consent to the study

b) Exclusion Criteria:

- a. Atypical medical history of Ménière's symptoms and questionable Ménière's diagnosis
- b. Bilateral Ménière's disease

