4. SUBJECT IDENTIFICATION, RECRUITMENT AND CONSENT

4.1. Method Of Subject Identification And Recruitment

Patients will be recruited from the clinical practice of the principal investigator.

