5. METHODS AND STUDY PROCEDURES

The screening visit may take place up to 30 days prior to the first study visit, or may occur on the same day as the first study visit. After providing informed consent, subjects will provide a complete medical and neuro-otological history/exam and the study team would review their standard of care Ménière's work-up. Because subjects are typically established patients of the PI, the history may be obtained retrospectively from the subject's chart.

At the screening visit and at each subsequent visit, the subject will complete the ‘Meniere’s functional level scale’ question (Appendix B).

At the first study visit (which might be the same day as the screening visit) the study team will confirm eligibility and the subject will be randomized to either the oscillation or placebo group, with the study team blinded as to which treatment is received. The study team will be informed whether Device A or Device B are to be used (see 7.2). For treatment, the subject will be in a private room at the Department of Otolaryngology Clinton Woods Clinic. The designated treatment device (oscillator or placebo) will be placed over the mastoid of their involved ear and secured via an elastic/Velcro headband. The subject is positioned so as to place the endolymphatic duct into a gravitationally dependent orientation (the subject lying on their contralateral side with the face slightly tilted towards the floor). The device is turned on and operated for 30 minutes. The subject will be periodically monitored by study staff during this time. Following each treatment, patients will be evaluated for response and untoward side effects.

Study visits 2, 3 and 4 will be 7 days apart. Prior to treatment, a thorough review of the behavior of the subject’s Ménière's disease over the preceding week as well as any sequelae of their treatment will be recorded. A complete ENT and neuro-otologic exam will be completed.

Study visit 5 will be two weeks following the final treatment visit (visit 4). Subjects will have a complete medical and neuro-otologic exam and be observed for short-term results of the treatments.

The final study visit will be three months after study enrollment. Subjects will have a complete medical and neuro-otologic exam and be observed for longer-term results of the treatments. Specifically, the frequency and severity of any Ménière's disease attacks will be recorded and compared to pretreatment patterns.

Schedule of Activities

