7. STUDY DEVICE

7.1. Study Device

The Mastoid oscillator is a small device (9 x 6 x 3 cm, ~200g see Appendix 1 for images) custom-made for the PI by Bridgekey Engineering Solutions of Rochester NY. It is secured with a Velcro elastic headband over the mastoid in the post-auricular region of the Ménière's affected ear. The contoured surfaces of the device ensure a smooth fit against the head and also no displacement of the ear. The placebo oscillator replicates the sound of the Mastoid oscillator but without the vibration to the skull. The device runs on a rechargeable battery and there is an on/off button. The start of vibration or sound is delayed by a few seconds after the device is turned on.

Between subject uses the device is cleaned with an alcohol wipe and stored by the study Research Technician in the Clinical Trials office of the ENT department at the Clinton Woods office, within a locked cabinet.

Note that this study is not intended to determine safety or effectiveness for commercial distribution of the oscillator or placebo oscillator. These are custom devices that are ordered by the principal investigator and are not generally available to other physicians. They are not generally available in finished form for purchase or for dispensing upon prescription and are not offered for commercial distribution through labeling or advertising. They are intended to meet the special needs of the principal investigator in the course of his professional practice.

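### Prior mastoid oscillation is not an exclusion, although the sham gives no vibration: a previously treated patient could enrol and would probably recognise it, and subject blinding is not assessed

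*Combined protocol and SAP*

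**What the plan says.** - **Sham.** Section 2.2: "This device will produce the sound of oscillation, but there will be no oscillation delivered". Section 7.1 agrees: "The placebo oscillator replicates the sound of the Mastoid oscillator but without the vibration to the skull". It adds: "The start of vibration or sound is delayed by a few seconds after the device is turned on".
- **Blinding.** Section 5 has subjects randomised "with the study team blinded as to which treatment is received", and section 7.2 supports this with coded devices and an allocation table held by the department chair. The subject's blinding rests on the matched sound; no other measure is described.
- **Recruitment.** Section 4.1: "Patients will be recruited from the clinical practice of the principal investigator". Section 5 notes that subjects are typically established patients there.
- **Earlier exposure.** Section 1.2 refers to a pilot "using head positioning and mastoid oscillation has been completed". Section 11.1 gives 66 treated patients and a control group of 30 with a delayed start. Whether the 30 are among the 66 is not stated.
- **Eligibility.** Section 3.2 has two exclusions: "Atypical medical history of Ménière's symptoms and questionable Ménière's diagnosis", and bilateral disease. Neither concerns earlier oscillation.
- **Outcome.** The primary outcome in 11.2 is the change in monthly vertigo episodes. Under 5.2 these are obtained by asking the subject about frequency and duration since the last visit.
- **Blinding check.** The visit text and schedule (5), the assessments (5.1, 5.2) and the analysis (11.2) include no question on which treatment the subject thinks was given.

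**The concern.** Sound is matched and touch is not. Each session lasts 30 minutes and there are four of them. The start delay of a few seconds does not hide whether the device later vibrates against the skull. A subject who has felt the real device has something to compare the sham with, and nothing in 3.2 keeps that subject out.

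The outcome is open to belief in two ways. Episode counts are self-reported. In addition, class F in 11.2 depends on a secondary treatment being started, and section 3.3 says these patients would otherwise be offered surgical or other procedures. A subject who infers sham may seek one sooner and be counted as a failure. Functional level, a secondary outcome, is also self-rated.

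At stake is how a positive result can be read. If some subjects recognised their arm, expectancy would compete with a device effect as the explanation, and the trial would hold no record of how far blinding had held.

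**Working it through.** **1. Can a previously treated patient enter?** Setting the sections side by side:

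- Recruitment is from the practice of the principal investigator (4.1). The pilot figures in 11.1 sum to 22 + 30 + 11 + 3 = 66 treated.
- Complete or substantial control was reached by 22 + 30 = 52, leaving 11 + 3 = 14 with limited or insignificant control. Later relapse among the 52 is not reported.
- A patient among the 14, or one who relapsed, could still meet the inclusion criterion of failed medical management, and neither exclusion would apply.
- The pilot was presented in 2002 and 2005 (references 2 and 3). No section says that pilot patients will or will not be approached, or that the pilot device was the same one.

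Entry is therefore possible but not shown.

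**2. The plan's own figure.** Section 11.1 gives 95% power for Fisher's exact test with 15 per arm, 75% against 12%, alpha 0.012. Exact enumeration gives 82.8% two-sided. This discrepancy is a separate matter, and nothing below depends on the 95%.

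**3. What belief alone could do (illustration).**

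Inputs: n = 15 per arm, Fisher's exact test, sham rate 12% and alpha 0.012, all from 11.1. Also 0.05 as the conventional level. Assumptions: no true effect, a two-sided test, response dichotomised as class A or B (11.1 does this for sample size; 11.2 does not specify it), and active-arm rates of 25%, 40% and 50% produced by belief. The documents give no expectancy effect.

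Formula: P(significant) = Σ C(15,a) p₁^a (1−p₁)^(15−a) × C(15,b) 0.12^b 0.88^(15−b), summed over all pairs (a, b) of active and sham responders with Fisher p ≤ alpha. For example, 5 against 0 gives p = 2 × C(15,5)/C(30,5) = 2 × 3003/142506 = 0.042, which counts at 0.05 but not at 0.012.

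| Reported A/B, active vs sham | at 0.05 | at 0.012 |
|---|---|---|
| 12% vs 12% (no bias) | 0.8% | 0.03% |
| 25% vs 12% | 6.5% | 1.0% |
| 40% vs 12% | 26.6% | 9.7% |
| 50% vs 12% | 46.5% | 24.8% |

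**4. How many previously treated subjects would that take?** Suppose device-naive subjects stay at 12% and, as an extreme, every previously treated subject in the active arm reports A or B. The share s needed solves s × 100 + (1 − s) × 12 = target, so s = (target − 12)/88:

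- 25%: 13/88 = 0.148, or 2.2 of 15 subjects
- 40%: 28/88 = 0.318, or 4.8 of 15
- 50%: 38/88 = 0.432, or 6.5 of 15

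A few previously treated subjects could produce the first scenario only. The larger ones need many such subjects, or belief effects in naive subjects too. The calculation holds the sham arm at 12%; lower reported response among subjects who recognise the sham would widen the gap.

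**The case against.** The strongest reply has four parts.

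- **Natural history is still addressed.** Section 2.2 frames the debate as whether improvement exceeds the natural course of the disease. A concurrent randomised control largely answers that even if some subjects guess their arm. This stands; expectancy is a separate question.
- **Naive subjects have no reference.** In a parallel-group design, a subject new to the device hears the matched sound with the unit strapped to the head and has no second sensation for comparison. What subjects are told to expect belongs to the consent form, which is not part of the text reviewed. This stands as a limit: unblinding of naive subjects is plausible, but its extent cannot be judged here.
- **Prior exposure may be rare.** The pilot is old, most of its patients did well, and section 2.2 says the debate blocks routine use of the treatment. This also stands, and it makes the exclusion cheap rather than unnecessary.
- **A guess question does not cure anything.** It measures unblinding without preventing it. Comparing response within guess categories would split 15 per arm on a variable observed after randomisation. This stands, so the question is offered only as optional description.

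A reader might go further and infer that an effect could not be separated from subjects knowing their arm, or that nothing collected could help. The documents do not support that. Enrolment of pilot patients is not shown, and knowledge of arm among naive subjects is not established. Hearing threshold and word recognition are named as secondary outcomes and are less open to expectation, although the schedule in section 5 lists no audiometry, so their support is limited.

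**Conclusion.** The point holds in a limited form. The sham differs from the active device in a way that can be felt, recruitment is from a practice whose principal investigator may already have treated eligible patients, and 3.2 does not exclude them. Such a patient would probably recognise the sham, and the self-reported primary outcome could be biased. Subject blinding is not assessed, so expectancy would remain a competing explanation for a positive result.

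The size is unknown. At the plan's alpha of 0.012, the mildest scenario (25% against 12%) gives 1.0%, still below the nominal level, while the 40% and 50% scenarios give 9.7% and 24.8%. These figures are conditional on an assumed expectancy effect and an A/B dichotomy; they do not estimate this trial's error rate. The case for acting rests on the gap in eligibility and the low cost of closing it.

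**What to change.** **Recommended.** Add one exclusion to 3.2: any prior mastoid oscillation treatment, in the pilot or otherwise. Check it from the chart and by asking the patient at screening. The cost is one line and the loss of a few otherwise eligible patients. The sham and the sample size are unchanged.

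**Optional.** Ask each subject one question (active, placebo, don't know) after the Visit 1 treatment and again at the final visit, and report the answers by arm in 11.2 as a descriptive table only. The early answer is needed because a late one is mixed up with response, and it cannot be recovered afterwards. The cost is one question at two existing visits. The table would show how far blinding held; it would not restore blinding or adjust the primary comparison.

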3. CHARACTERISTICS OF THE RESEARCH POPULATION

3.1. Subject Characteristics

- a) **Number of Subjects:** We plan to enroll up to 40 subjects in order to accrue 15 randomized to the treatment arm of the study and 15 assigned to the placebo/control arm.
- b) **Gender and Age of Subjects:** Subjects 18 years of age and older will be included in the study and there will be no restriction on gender.
- c) **Racial and Ethnic Origin:** There will be no restriction based on race or ethnicity.

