4.2. Process of Consent

If eligible, patients will be approached by the PI to discuss the study. Candidate subjects will be assured that their decision to participate or not to participate will not affect the medical care that they can expect. If they are interested in participation, they may take the consent form home or they may provide consent at that time. When ready to consent, the teach-back method will be used to ensure that the subject understands their participation in the study. Preferentially, consent will be obtained by study personnel other than the PI, however due to logistics this may not be possible or convenient to the subject, in which case the PI may obtain consent.

Consent will be documented in a consent log in REDCap and signed forms will be stored in the Otolaryngology Department Research Office (SMH 1.5010). The subject will receive a copy of the signed form.

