6. SUBJECT WITHDRAWALS

Subjects will be advised in the written informed consent forms that they have the right to withdraw from the study at any time without prejudice. Subjects will be withdrawn from the research without their consent by the investigator if they are non-compliant (miss scheduled study visits), or if the investigator determines that it is in the best interest of the subject. Also if the subject develops bilateral Ménière's disease during the study they will be withdrawn. There are no additional study activities requiring completion prior to subject withdrawal from the study. Subjects withdrawn from the study will not be replaced.

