11. DATA ANALYSIS AND MONITORING

11.1. Sample Size Determination

The pilot study^{2,3} showed that mastoid oscillation treatment was highly efficacious. Of 66 subjects that were treated, 22 (33.3%) achieved complete control, 30 (45.4%) achieved substantial control, 11 (16.7%) achieved limited control and three (4.5%) had insignificant control. A control group (N=30) with delayed start of treatment had just 2 subjects with improvement of symptoms (complete or substantial) during the wait period (6.6%).

For our sample size projection, we assume that the Mastoid Oscillation arm will have a 75% rate of achieving substantial or complete control, and 12% for the placebo group. With 15 subjects in each group, using Fisher's Exact test, the design has 95% statistical power with alpha of 0.012.

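### Section 11.1 claims 95% power with 15 per group, but its own inputs give 82.8% (two-sided) or 86.8% (one-sided), and nothing is allowed for withdrawals

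*Combined protocol and SAP*

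**What the plan says.** Section 2.1 sets the ratio: "Eligible subjects will be randomized using a 1:1 allocation". Section 3.1 gives the ceiling and the target: "We plan to enroll up to 40 subjects in order to accrue 15 randomized to the treatment arm of the study", with the same number on placebo. No section says what the ten enrolments above 30 are for.

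Section 11.1 gives the assumed rates: "we assume that the Mastoid Oscillation arm will have a 75% rate of achieving substantial or complete control, and 12% for the placebo group". It then states the result: "With 15 subjects in each group, using Fisher's Exact test, the design has 95% statistical power with alpha of 0.012". It does not say whether the test is one- or two-sided, or why alpha is 0.012. It gives no dropout rate.

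Section 6 lets the investigator withdraw subjects, for example for missed visits or newly bilateral disease, and adds: "Subjects withdrawn from the study will not be replaced".

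**The concern.** Section 11.1 names the test, both rates, the group size and alpha, so its power can be checked exactly. It does not come out at 95%. On a two-sided reading the chance of missing the assumed effect is 17.2% (100 − 82.8), more than three times the stated 5%.

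The gap between 40 and 30 could also be taken for a reserve against dropout. With the randomised number fixed at 15 + 15 and replacement barred, it cannot serve that purpose. A subject lost after randomisation comes out of the 30. Follow-up runs to day 90 and missed visits are a reason for withdrawal, so some loss is plausible, and the power statement makes no provision for it.

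At stake is whether those approving and running the trial know what 30 randomised subjects can show.

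**Working it through.** **Inputs.** Control rates 0.75 and 0.12, Fisher's exact test, 15 per group, alpha 0.012 and stated power 95% are all from section 11.1. Sidedness is not stated, so both readings are computed. The outcome is complete or substantial control against anything else, as section 11.1 frames it.

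**Formula.** Power = Σ over all pairs (x, y) of Bin(x; n, 0.75) × Bin(y; n, 0.12), counting only pairs for which Fisher's p ≤ alpha. Here x and y are the numbers controlled on oscillation and placebo.

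**Step 1: the plan's own figure (n = 15, two-sided, alpha 0.012).** For each y, find the smallest x that is significant, then multiply P(y) by P(X ≥ that x).

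| y on placebo | smallest significant x | P(y) | P(X ≥ x) | product |
|---|---|---|---|---|
| 0 | 7 | 0.1470 | 0.9958 | 0.1464 |
| 1 | 9 | 0.3006 | 0.9434 | 0.2836 |
| 2 | 10 | 0.2870 | 0.8516 | 0.2444 |
| 3 | 11 | 0.1696 | 0.6865 | 0.1164 |
| 4 | 12 | 0.0694 | 0.4613 | 0.0320 |
| 5 | 13 | 0.0208 | 0.2361 | 0.0049 |
| 6 | 14 | 0.0047 | 0.0802 | 0.0004 |

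The products sum to 0.8281, and larger y adds nothing at this precision. Power is **82.8%**, not 95%. The one-sided test at 0.012 gives **86.8%**.

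**Step 2: could another convention explain 95% at n = 15?**

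- Fisher at alpha 0.05: 92.0% two-sided, 96.5% one-sided.
- Chi-square at 0.012, enumerated exactly: 91.6% two-sided, 93.1% one-sided.
- Normal approximation at 0.012: 89.5% two-sided, 94.3% one-sided. The last is close, but it is not the named test.
- Reading 0.012 as the attained size of a one-sided 0.05 Fisher test: that size is 0.016 at a common rate of 12% and at most 0.022, so this does not match either.

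**Step 3: could other inputs explain it?** Two routes give about 95% with two-sided Fisher at 0.012:

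- 20 per arm with 75% against 12%: 94.98%.
- 15 per arm with the pilot rates in section 11.1, (22 + 30)/66 = 52/66 = 78.8% against 2/30 = 6.7%: 95.7%.

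One-sided Fisher at 18 per arm (75% against 12%) also gives 94.8%. The documents do not say which of these, if any, was used.

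**Step 4: effect of lost outcomes.** The number lost is an assumption. Two-sided Fisher, 75% against 12%:

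| Usable per arm | alpha 0.012 | alpha 0.05 |
|---|---|---|
| 15 | 82.8% | 92.0% |
| 14 | 75.6% | 90.4% |
| 13 | 70.9% | 91.2% |
| 12 | 63.0% | 86.6% |

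The slight rise from 14 to 13 at alpha 0.05 reflects the discreteness of the exact test. Losing two per arm costs 82.8 − 70.9 = 11.9 points at 0.012, but only 92.0 − 91.2 = 0.8 points at 0.05.

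**The case against.** The strongest reply is that the sample-size rules are consistent and the trial is adequately sized. Much of this stands.

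- A reader might infer that sections 3.1 and 6 contradict each other. They do not. Enrolling up to 40 to randomise 30 is an ordinary screening allowance. It is true that section 4.2 says "If eligible, patients will be approached by the PI to discuss the study", and that screening may fall on the day of Visit 1. But section 5 puts consent before the history, examination and work-up review, allows up to 30 days before Visit 1, and confirms eligibility there. Barring replacement is a legitimate choice.
- A reader might infer that the 95% was computed for 20 per arm, that is, for the 40. The numerical match is close, but the pilot rates at 15 per arm fit about as well. Sections 3.1 and 11.1 both say 15, and no section says 20.
- A reader might infer that fewer than 15 per group will be analysed. No section removes withdrawn subjects from the analysis, vertigo is documented at every study visit, and class F in section 11.2 counts secondary treatment as an outcome. A loss of usable outcomes is a possibility, not a stated consequence.
- At a conventional two-sided 0.05 the design has 92.0% power and is little affected by losing two per arm. That is a fair limit on how serious the point is. It does not rescue the sentence in section 11.1, which states 0.012.

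None of these replies makes 95% correct for the inputs printed beside it.

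**Conclusion.** The power statement in section 11.1 is wrong as written. With 15 per group, 75% against 12%, Fisher's exact test and alpha 0.012, power is 82.8% two-sided or 86.8% one-sided, a shortfall of about 12 or 8 points (95 − 82.8 = 12.2; 95 − 86.8 = 8.2). The source of the 95% cannot be determined from the documents.

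No allowance for withdrawals is built in. The ten enrolments above 30 can offset only losses before randomisation. How much this matters depends on the alpha that will actually be used: two lost outcomes per arm would leave 70.9% at 0.012 but 91.2% at 0.05, both two-sided.

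These figures rest on the plan's assumed rates, on a comparison of complete or substantial control against the rest, and on an illustrative loss. They do not show a badly underpowered trial, nor do they support raising the randomised number to 40. That would put up to ten more subjects through treatment and leave no room for screen failures under the ceiling of 40. It would also reach 95% only if nobody were lost.

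**What to change.** Keep 15 per arm and rewrite the last sentence of section 11.1 so that it does three things:

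1. States the sidedness and the alpha that will be used for the primary test.
2. Gives the matching power: about 83% at two-sided 0.012, or 92% at two-sided 0.05.
3. Adds the power at the number expected to have a final-visit outcome, with the assumed loss stated. For example, 13 per arm would give 70.9% at two-sided 0.012 or 91.2% at two-sided 0.05.

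The choice of alpha should be made and recorded before the blind is broken, and not because one value yields the better figure.

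The cost is a change of wording in one section. No more subjects are enrolled or treated, and the ceiling of 40 and the rule on replacement can stay. The downside is that the stated power becomes less favourable.
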